1.6 Progress plan

Recruitment: Q1, 2020 – Q1, 2021

Intervention and follow-up: Q2, 2020 – Q1, 2022

End of trial: Q2, 2022

The trial will be conducted in compliance with the protocol, ICH GCP guidelines and the applicable regulatory requirements and in accordance with the Brazil (2013) amendment to the Declaration of Helsinki 1964.

2. SYNOPSIS

Latent autoimmune diabetes in adults (LADA) is a common type of diabetes which often masquerades as type 2 diabetes because patients clinically do not need insulin for a significant time period after diagnosis. Still these patients progress with time in large numbers to insulin dependency; this is due to the impact of autoimmunity, which is manifested by positivity for type 1 diabetes-like antibodies, in particular anti-GAD (GADA). Our recently completed 21 month clinical trial (BALAD) shows that patients displaying high levels of GADA successively lose their capacity for insulin secretion regardless of tested treatment alternatives (insulin before clinically needed or a DPP-4 inhibitor, both as add-ons to metformin). Treating autoimmunity directly is thus needed to halt diabetes progression in these high GADA titer LADA patients.

Therefore, together with co-investigators at Karolinska University Hospital ([name]) and Linköping University ([name]) we propose a vaccination study testing for desensitization of the autoimmune process by intra-inguinal injections of GAD-alum. Encouraging results from a pilot study in type 1 diabetic children and adolescents support the rationale for a similar study in LADA.

We plan to enroll approximately 15 patients newly diagnosed with LADA and who display high levels of GADA to receive three intra-inguinal injections of GAD-alum one month apart. The company Diamyd Medical AB (Stockholm) will collaborate by providing the GAD-alum to be injected. We will follow patients during one year for safety (no safety concerns were raised in the afore-mentioned study) and immunological, mainly T-cell, responses. In addition, we will follow beta cell function as tested by C-peptide glucagon and mixed meal tolerance tests.

The study is a pilot one that does not include a placebo arm. A positive outcome (no safety concerns, a robust immunological response and a favorable time course of beta cell function compared to a historical control, i.e. BALAD, will pave the way for a placebo-controlled phase II/III study.

3. INTRODUCTION

3.1 Investigational medicinal product

The investigational product in this trial is GAD-alum (Diamyd®). The active ingredient is recombinant human glutamic acid dehydrogenase (rhGAD65), formulated in aluminium hydrogel. GAD-alum will be available from the company Diamyd Medical AB in Stockholm, Sweden.

3.2 Non-investigational medicinal product

The non-investigational medicinal product in this trial is vitamin D (1 tablet/day, total daily dose of 2000 IE) given per os from day -30 through day 90.

Trade name: "Divisun 2000 IE", Supplier: Study site Stockholm: Meda, Solna, Sweden.
Study site Trondheim: Meda, Allerød, Denmark.

3.3 Background and rational

3.3.1 *Urgent need for a treatment that counters autoimmunity in LADA*

Latent Autoimmune Diabetes in Adults (LADA) encompasses approximately 10% of phenotypic type 2 diabetic patients [1]. LADA patients are by definition not insulin dependent at diagnosis. However, very many of these patients experience a successive decline of their own insulin secretion, something that renders these patients insulin dependent within a few years. The demise of LADA patients' insulin-producing beta cells is due to an autoimmune process that is similar to the autoimmune process in type 1 diabetes. The speed of beta cell demise is coupled with high levels of type 1 diabetes-like antibodies, in particular to antibodies against glutamic acid decarboxylase (GADA), which likely reflect the intensity of the autoimmune process [2, 3].

There is strong evidence that demise in beta cell capacity to release insulin couples to deterioration of metabolic control and that such deterioration in turn leads to an increased risk for complications of diabetes with serious consequences in terms of morbidity and mortality [4, 5]. In addition, reports indicate that LADA patients have worse metabolic control than other types of diabetes when comparing mortality [6, 7]. Consequently, there is an urgent need for therapies that counteract the ongoing destruction of beta cells in LADA patients. LADA is – as indicated above – a very common form of diabetes; this underscores the need for a therapy that works.

Very few studies, only 10 clinical trials listed on clinicaltrials.gov, have specifically investigated the extent to which different types of treatment could influence the decline of beta cell function in LADA patients (Clinicaltrials.gov as of February 15th 2019). The scarcity of trials and the resulting lack of evidence for best treatment in LADA has led to large regional variations in treatment.

In the recently published BALAD trial [8] we randomized LADA patients to add-on treatments with either insulin (primarily nighttime NPH insulin, i.e. intermediate acting insulin) or a DPP-4 inhibitor, sitagliptin (trade name Januvia), 100 mg daily. Here we show that early insulin treatment does not provide any added benefit when compared to sitagliptin. Further, following patient stratification at inclusion into low and high GADA titer groups, (cutoff 190 U/ml) results show a clear deterioration of stimulated C-peptide parameters in participants in those of the high GADA category. The decline in stimulated C-peptide amounted to a median of 38% compared with results obtained at the time of randomization.

Taken together these findings demonstrate the inability of standard therapeutic modalities to modify the impact of autoimmunity in LADA. We conclude that a new therapy is needed that directly counters autoimmunity in LADA patients displaying high titers of GADA.

3.3.2 GAD-vaccination – an alternative to other immunotherapies?

In the type 1 diabetes field, several immunomodulatory therapies have included both children at high risk to develop type 1 diabetes and children or adolescents with recent onset of the disease. Immunotherapies include testing the effects of antibodies against CD3 or CTLA-4 (abatacept). The results have been mixed, with trials showing no positive effects, and others showing improvement of insulin secretion (as assessed by stimulated C-peptide measurements). In general, beneficial effects have been short-lived and side effects frequently encountered [9].

Could a vaccination study with GAD provide an alternative to other trials that modulate diabetes-associated autoimmunity? Antigen therapy aims at presenting the antigen to the T-cells in the lymph nodes to get a new balance of the immune system and tolerance against the antigen. GAD can be regarded as an auto-antigen, as it is produced in the pancreatic islets from which this protein is released in response to beta cell stimulation. Hence, the effect of GAD-vaccination is achieved through antigen-specific reprogramming of immune cells to create tolerance to GAD rather than causing beta cell demise.

Studies have shown that administration of GAD can prevent diabetes in experimental animals [10]. The observed effect, which was observable even after the start of the autoimmune process, suggests that it might be possible to expect the same effect in humans.

3.3.3 Previous and ongoing GAD-vaccination trials

In a phase II study in LADA patients the subcutaneous administration of one low dose of GAD-alum, 20 µg, led to improved beta cell function for up to 2 years compared to the placebo treated group, with no side effects [11]. In addition, other doses were tried: 4 µg showed no effect, 100 µg showed a similar effect as 20 µg, while 500 µg showed no effect. None of the doses were associated with any adverse events. An association with changes in the ratio of CD4+CD25+/ CD4- CD25- cells was found, indicating a mechanism behind the beneficial effect [11].

These findings were followed up by a phase II study in children and adolescents with type 1 diabetes, which also showed beta cell preserving effects by subcutaneous GAD-alum injections. However, a phase III study did not reproduce these findings [12]. Further analysis of results from the phase III study indicated positive effects in subgroups of participants [13]. A meta-analysis of studies with subcutaneous GAD-alum injections showed altogether a positive effect on C-peptide parameters; these effects were however only modest and of questionable size to pursue [14].

However, the subcutaneous route of injection may be inferior to other routes in activating the desired immunological pathways. Desensitization studies in allergy patients indicate that intralymphatic injections of antigen achieve desensitization better than other types of injections [15]. As this route of administration has the potential to maximize the immune response, lower doses of the allergen can be used. Inguinal lymph nodes are readily accessible in patients and are chosen as the site of administration of the GAD-alum.

Results with intranodal injections of GAD-alum are available from a 15-month proof-of-concept phase I/II clinical trial DIAGNODE-1 (NCT02352974) [16]. DIAGNODE-1, is an open-label trial of intralymphatic rhGAD therapy together with vitamin D supplementation for 12 patients aged 12 to 24 with residual beta cell activity diagnosed with type 1 diabetes within six months of inclusion. This study employs three low doses (4 µg each) of GAD-alum that are administered directly into an inguinal lymph node using ultrasound guided injections. The disease progression appears very positive in terms of partial remission, levels of stimulated C-peptide, HbA1c and insulin dose. Using the compound variable insulin dose-adjusted HbA1c (IDAAC) as a marker, 11 of 12 patients attained partial remission after 15 months (IDAAC \leq 9) ([name], unpublished data). In comparison, less than 20% of children and adolescents with new-onset T1D in a cohort (N=3657) followed over six years were in partial remission 18 months after diagnosis [17].

After 15 months, stimulated C-peptide area under the curve (AUC) decreased by only 19% in treated patients. In contrast, a matched untreated control population of 27 patients (historical controls) selected from the placebo arm of a different Diamyd trial in the same patient age-range showed an average decrease of between 40% and 50% [18]. The positive effects on beta cell function reported in the DIAGNODE-1 trial are accompanied by a reduction in HbA1c by 18% (compared to a 15% increase in controls), and average insulin dose increase of only 6% (compared to more than a 50% increase in controls) ([name], unpublished data).

Immunological response to intralymphatic administration was characterized by a relative reduction of IgG1, with a shift towards IgG2, IgG3 and IgG4 subclasses after 3 intra-lymphatic injections of GAD-alum ([name], unpublished data). This finding is significant as both IgG2 and IgG4 have low respectively no ability to bind complement and an IgG4 response is associated with long-term immunotherapy response in the allergy field [15]. Further, while IgG1 is the dominant GAD antibody subclass in type 1 diabetes, IgG4 is more common in

LADA, suggesting that subclass distribution is an important aspect of the underlying disease mechanism [19].

Importantly, comparing a few patients in the DIAGNODE-1 trial to patients that had received a subcutaneous injection of GAD-alum, indicate that the clinical effects correlate with an immune response which is stronger and more pronounced in its Th2 responses than that from subcutaneous GAD-alum administration [20].

3.3.4 Rationale for the use of GAD-alum in the treatment of LADA

A large part of LADA patients will within a few years after diagnosis develop a need for insulin treatment. Exogenous insulin cannot cure diabetes, neither does it represent an ideal therapy, as even well-treated and monitored patients develop significant complications and have increased morbidity and mortality. A therapy that could counteract beta cell demise completely, or at least to an extent so that levels of blood glucose could be kept in the normal range, is therefore highly desirable.

The underlying pathology in type 1 diabetes and LADA is thought to be closely similar. Also, type 1 diabetes and LADA seem genetically similar, in that they share the same frequency of HLA genes conferring either susceptibility or protection to type 1 diabetes [21]. However, type 1 diabetes and LADA do represent two separate sub-groups of autoimmune diabetes. Differences between the two subgroups, like the age of onset (for type 1 diabetes usually in childhood/youth years vs. for LADA most often after 35 years of age) and the intensity of autoimmunity, might impact on the response to the GAD-vaccine. Hence, safety and feasibility of intranodal treatment with GAD-alum has to be confirmed also in LADA individuals in order to support a larger trial in the LADA population.

The proposed trial will be the first to test for the effect of intranodal injections of GAD-alum in LADA subjects. The study is a unique one and has the potential to provide a therapy that halts or delays autoimmunity-governed beta cell destruction in LADA patients.

3.3.5 Rationale for vitamin D supplementation

Oral vitamin D supplementation will be given only to those patients with vitamin D levels below 100 nmol/L at the screening visit.

Experimental evidence indicates that vitamin D may play a role in the defense against type 1 diabetes through its effects on the immune system. Vitamin D has been shown to affect antigen presenting cells (APCs) and T-cells in such a way that an anti-inflammatory and Th2 inclined immune response is favored, including an increase in the T-regulatory cell response and the secretion of IL-10 [22] [22-25]. Mechanistic studies have shown that vitamin D modulates dendritic cell maturation in vitro and in vivo [26-29], facilitates a shift from a Th1 to a Th2 immune response [30], and promotes a switch from M1 to M2 macrophages [31]. Because of these properties, vitamin D has been used e.g. in cell therapy protocols to produce tolerogenic

immune cells. Vitamin D has further been shown to direct the immune response to a GAD65 peptide from a Th1 towards a Th2 profile in NOD mice [32].

Pre-conditioning with vitamin D is intended to avoid the negative impact of vitamin D insufficiency on the tolerogenic effect of the antigen specific Diamyd immunotherapy.

3.4 Safety and feasibility of GAD-vaccination together with vitamin D supplementation

In contrast to traditional immune suppression, GAD-alum treatment (administered subcutaneously or intralymphatic) is regarded as safe, very tolerable and with little or no discomfort for the patients. No treatment-related adverse events of GAD-alum have been reported except from mild and transient reaction at the injection site. Also, intralymphatic injections are reported as less painful than a venous puncture [16, 33].

Vitamin D in a dose of 2000 IU/day in children has been reported safe [34]. Additionally, a dose of up to 7000 IU/day given to children from 5 years of age with human immunodeficiency virus (HIV) did not raise any safety concerns [35]. We do not foresee that the vitamin D supplementation to the GAD-alum treatment would increase the theoretical risks of GAD-alum, such as acceleration of the autoimmune process, undesirable effects on the immune system, or neurological disease.

3.5 Choice of study drug administration and dosage

As mentioned, studies in allergy immunotherapy show that, compared to other routes of administration, injections of antigens directly into the lymph nodes leads to better efficacy of the treatment [15]. Encouraging results from the DIAGNODE-1 trial (see Section 3.3.3) as well as unpublished blinded safety data from an ongoing phase II trial (DIAGNODE-2, NCT03345004) in type 1 diabetes ([name], personal communication) support the rationale for a similar study in LADA. Based on the experiences from DIAGNODE-1 and -2, we will in the proposed trial use the same route of administration, dosage and treatment intervals as in the DIAGNODE trials (for details, see Section 7.1 and Table 1). The DIAGNODE-1 trial shows that potential treatment-related changes in the immunological parameters of interest are detectable within 12 months from baseline. The total study period from baseline in the proposed trial will therefore be 12 months.

3.6 Study population

Study participants are to be men and women between 30-70 years of age, that have been diagnosed with LADA within the last 18 months, i.e. being GADA positive and insulin independent at baseline. Based on the findings in our recent trial, BALAD (see 3.3.1), we will include only those with high GADA titers (>190 U/ml).

Altogether approximately 15 LADA patients will be recruited from one clinic in Norway (St Olavs Hospital, Trondheim) and one in Sweden (Karolinska University Hospital, Stockholm). Recruitment will be through advertisement in journals for diabetic patients and information through other media outlets as well as by referrals from physicians treating patients for

diabetes. Given that LADA patients constitute 10% of the total diabetes population we foresee that the study will be fully recruited within 1 year.

4. TRIAL OBJECTIVES AND PURPOSE

The purpose of the trial is to evaluate the effects of 3 intra-nodal injections of GAD-alum, together with oral vitamin D supplementation, in a population of LADA patients with high GADA titers. Effects will be summarized at 5 and 12 months after the first injection.

- The primary objective is to evaluate safety and feasibility of this treatment regimen.
- Secondary objectives are to test if the treatment induces a strong GAD-specific immune response similar to what has previously been observed in type 1 diabetes patients and to test for indications of preservation of endogenous insulin production.

The pilot study will be performed in order to support the launch of a larger placebo controlled clinical trial in the LADA population.

5. TRIAL DESIGN

5.1 Primary endpoint

Variables for the evaluation of safety and feasibility:

- 1) Injection site reactions, skin reactions 1 hour post injection vs. before injection.
- 2) Occurrence of AEs, continuously registered and status summarized at 5 and 12 months after the first injection.
- 3) Laboratory measurements (hematology and clinical chemistry), status summarized at 5 and 12 months after the first injection vs. baseline.
- 4) Physical examinations, including neurological assessments, status summarized at 5 and 12 months after the first injection vs. baseline.
- 5) GAD65A titer in serum, levels at 5 and 12 months after the first injection vs. baseline.
- 6) Vital signs (blood pressure), status summarized at 5 and 12 months after the first injection vs. baseline.

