- b. The GAD-alum injection directly into the inguinal lymph node is to be done by an appropriately qualified radiologist at the X-ray department at the study site by help of ultrasound technique.
- c. On day two at visit 2, the glucagon test needs to be done before the injection of GAD-alum.
- d. Supplementation with vitamin D starts at day -30, after the glucagon test has been performed, if the vitamin D serum levels are below 100 nmol/L (40 ng/ml) at screening. If the patient has vitamin D serum levels above 100 nmol/L (40 ng/ml) at screening, no Vitamin D supplementation will be given for that patient.
- e. The investigator/study nurse will inspect the injection site before and after the injection is given and record any injection site reactions in the Case Report Form (CRF).
- f. The MMTT and the Glucagon test must be carried out on separate days, as each test has to be performed in the fasting state.
- g. Antibodies against IA-2 (islet cell antigen 2), ZnT8 (Zink transporter 8) and insulin will be measured at Baseline and at Visit 7.
- h. Antibodies against SARS-CoV-2 will be measured at Visit 6 and Visit 7.

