7. TREATMENT AND FOLLOW UP

7.1 Study drug: dosage and interval

Enrolled participants will receive an intra-nodal injection of 4 µg GAD-alum three times. The first, second and third injection will be 1 month apart (Table 1). GAD-alum will be injected directly into an inguinal lymph node by a qualified radiologist at the X-ray department of the study site by help of ultrasound technique. The responsible investigator or study nurse will inspect the injection site prior to administration of GAD-alum. The patient shall remain in the vicinity of the study site for the next hour after the injection, and the injection site will be investigated again by the responsible investigator or study nurse 1 hour post injection. Attempts will be made to inject GAD-alum into the same lymph node each time. The time of the day for injection will be decided by the cooperating radiologist.

Supplementation with vitamin D starts at day -30 if the vitamin D serum levels are below 100 nmol/L (40ng/ml) at screening. If the patient has vitamin D serum levels above 100 nmol/L (40 ng/ml) at screening, no vitamin D supplementation will be given to that patient. Patients with vitamin D levels below 100 nmol/L (40 ng/ml) at screening will receive vitamin D (2000 IE per day) administered orally for 4 months (120 days in total). The patient should be instructed to return all unused vitamin D blisters/boxes at Visit 6.

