13.1 Risk-benefit analyses

LADA cannot be cured and can hardly be prevented. A treatment that preserves the insulin secreting capacity of the LADA patient's beta cell, or at least decelerate the demise of beta cells, would be of great value for the patient (see also Section 3.3.1). A better preservation of beta cell function would result in better metabolic control, leading to lesser diabetic complications and thus a better self-management of their disease, i.e. an improved quality of life.

Any immune intervention in LADA patients must balance the possible benefits with any negative effects. One could argue that the increasing therapeutic possibilities for treatment of LADA (and other types of diabetes) that have emerged in recent years (such as new drugs and better possibilities for self-monitoring of blood glucose) will to some extent diminish the possible benefits of immune intervention in terms of better glucose control and better quality of life. In the face of better standard treatment for diabetes now than in previous years it becomes more important than ever that side effects (both short-term and long-term) do not overshadow benefits of treatment. Such would be the case if strong immune suppressants used in other autoimmune diseases (think rheumatoid arthritis or multiple sclerosis) would be administered. Long-term experience from vaccination with GAD-alum has so far shown negligible side effects [16, 33] (for details, see Investigator's Brochure), this being in contrast to most other agents that have so far been used to prevent beta cell deterioration in type 1 diabetes. Vaccination with GAD-alum would therefore seem to present an ideal way to intervene in LADA patients.

Some patients may balk at the prospect of injections given in lymph nodes rather than subcutaneous injections. However, experience in children and adolescents in previous and the ongoing trial (DIAGNODE-2) using this new mode of administration are favorable: no adverse events or added discomfort compared with subcutaneous injections (only mild transient reactions to the site of injection). The pain associated with the injections is reported to be less than taking intravenous blood samples. This will be thoroughly explained to potential study participants.

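### Primary variable 1 names only skin reactions after a lymph-node injection, and groin tenderness, swelling and pain are not solicited at the checks already made

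*Combined protocol and SAP*

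**What the plan says.** The injected tissue is stated plainly in section 7.1: "GAD-alum will be injected directly into an inguinal lymph node by a qualified radiologist". The first primary variable in section 5.1 is "Injection site reactions, skin reactions 1 hour post injection vs. before injection". It opens with a general term, but skin is the only content it names.

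The assessment is described in three places:
- Table 1 labels the procedure an inspection of the injection site.
- Footnote e to Table 1 reads "The investigator/study nurse will inspect the injection site before and after the injection is given and record any injection site reactions", with the result entered in the CRF.
- Section 7.1 says, for the check before injection, "The responsible investigator or study nurse will inspect the injection site prior to administration of GAD-alum", and for the later one, "the injection site will be investigated again by the responsible investigator or study nurse 1 hour post injection".

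Other primary variables in section 5.1 also bear on local reactions. Adverse events (item 2) are registered on an ongoing basis and summarised at 5 and 12 months. Physical examination (item 4) is summarised at the same two times. The adverse event definition in section 9.2 is wide enough to include node swelling, tenderness or pain.

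On pain, section 13.1 states: "The pain associated with the injections is reported to be less than taking intravenous blood samples". Section 3.4 makes a similar statement from cited work. Neither section 5.1 nor section 5.2 lists a pain variable.

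**The concern.** Section 4 makes safety and feasibility the primary objective. Section 3.3.4 says both must be confirmed for the intranodal route in LADA and describes this as the first such trial. Section 3.4 says the only treatment-related events reported so far are mild, short-lived reactions at the injection site. Variable 1 therefore covers the one kind of reaction the protocol expects, yet its stated content is the skin over the needle track rather than the node or the groin.

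The absence of safety concerns is part of the positive outcome that would lead to a placebo-controlled trial (section 5.3). If few or no reactions are reported under item 1, a reader needs to know whether tenderness, swelling and pain were looked for and not found, or not looked for. The two sites have no shared definition in the protocol that would answer this. The intranodal experience cited comes from patients aged 12 to 24 (section 3.3.3) and from children and adolescents (section 13.1), whereas this trial enrols adults aged 30 to 70.

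**Working it through.** The plan gives no reaction rate, grading scale or power figure for this variable, so there is no stated number to reproduce. The check compares the passages and then takes intervals from Table 1.

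**Step 1. What each passage specifies**

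| Place | Content named | Method named | Tenderness, swelling or pain asked for? |
|---|---|---|---|
| 5.1 item 1 | Skin reactions | Not given | No |
| Table 1 row | Injection site | Inspection | No |
| Table 1 footnote e | Any injection site reaction | Inspection before and after | No, but not excluded |
| 7.1, before injection | Injection site | Inspection | No |
| 7.1, at 1 hour | Injection site | Not specified | No |
| 5.1 item 2 with 9.2 | Any unfavourable sign or symptom | Recorded by the physician at each visit (9.1) | Not solicited, but would qualify |
| 5.1 item 4 | Physical and neurological examination | Not given | No groin examination named |

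The three descriptions of the site check do not match. Item 1 points to skin, footnote e is broader, and section 7.1 leaves the 1-hour method open.

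**Step 2. When adverse event recording next comes round**

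Inputs from Table 1, nominal days: injections on days 2, 30 and 60; adverse event records on days 1, 30, 60, 150 and 360. The record for the first injection visit is on day 1, before the injection. At the second and third injection visits the record falls on the injection day, and the plan does not say whether it is taken before or after the 1-hour check. The next record on a later day is:

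- Injection 1: 30 − 2 = 28 days
- Injection 2: 60 − 30 = 30 days
- Injection 3: 150 − 60 = 90 days

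The visit windows move these. For injection 3, with ±5 days on day 60 and ±14 on day 150, the range is (150 − 14) − (60 + 5) = 71 to (150 + 14) − (60 − 5) = 109 days.

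**Step 3. How many injections are affected**

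15 patients × 3 injections = 45 injections at most. This counts occasions on which the protocol does not specify these items. It does not count missed reactions.

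**The case against.** The strongest reply is that node reactions are already inside the primary evaluation. Item 1 begins with a general term, footnote e covers any reaction, and section 7.1 does not restrict the 1-hour check to looking. Swelling or pain meets the adverse event definition. It would be graded for severity and relationship (section 9.4) and tabulated by body system, causality and severity (section 10.1). The CRF is not among the documents and may list components. The pain statements report earlier experience and are not hypotheses of this trial.

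Most of this stands, and it rules out several stronger readings that a reader might infer:

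- That variable 1 cannot capture node reactions. Footnote e contradicts this, and the word visual does not appear in the description of the check.
- That such reactions surface only if patients volunteer them. The plan does not say how adverse events are elicited.
- That ultrasound information on the node is thrown away. The documents do not say what the radiologist records. Section 7.1 says "Attempts will be made to inject GAD-alum into the same lymph node each time", which suggests that some record of the node is kept.
- That node diameter should become an endpoint. There is no comparator or interpretation rule, it adds a measurement, and a scan about 30 days after the previous injection would largely miss reactions the protocol describes as short-lived.

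What the reply does not supply is a definition. Adverse event capture has no planned comparison of the groin before and after injection, and a mild reaction may have to be recalled weeks later.

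**Conclusion.** The point holds in a limited form. Variable 1 names only skin reactions, the three descriptions of the check do not agree, and no passage solicits groin tenderness, swelling or pain. Such reactions remain reportable as adverse events, so the weakness is less reliable capture and not exclusion. With the next scheduled adverse event record about 28, 30 and 90 days after the three injections, mild local reactions may be under-counted across up to 45 injections. The amount cannot be estimated, because the documents give no rate or duration for node reactions.

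This rests on three assumptions: that the nominal Table 1 days apply, that the CRF does not already list these items, and that the table as extracted is complete (it shows a neurological assessment row but no general physical examination row). If the CRF does list them, what remains is to bring the protocol wording into line with it. The change is worth making because local safety of this route is central to the trial and the staff checks already take place.

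**What to change.** Redefine item 1 in section 5.1 as local injection-site reactions, with three components: skin; groin tenderness or swelling; and pain. At the existing pre-injection and 1-hour checks, record palpation findings for tenderness and swelling (yes/no) and a 0–10 pain score. Report the share of injections with each component, beside the adverse event tables. Align sections 5.1 and 7.1, the Table 1 row and footnote e so that all describe the same assessment. As an optional feasibility item, the radiologist could note the side and whether the same node was used.

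The cost is a few CRF lines and a brief palpation and pain question at checks staff already make, with no new visit, scan or staff. The local-reaction count will probably look slightly less favourable, and it will include tenderness caused by the needle, which a single-arm trial cannot separate from a reaction to the product. The report should say so.
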